This study addresses these limitations. We will collaborate with 10-12 home visiting (HV) programs serving primarily low-income women. HV is an ideal setting for this study given the large numbers of perinatal women they serve and will build on the PI's existing relationships with HV programs in Illinois. In Phase 1, we will recruit 108 pregnant women for a RCT in which half the participants will receive MB and half will receive MB with a text message enhancement (MB-TXT). MB-TXT will provide reinforcement of key MB skills that are linked to hypothesized mechanisms of change, promote completion of MB personal projects (homework), and facilitate self-monitoring of one's mood. In Phase 2, we will recruit 36 mother-father dyads for an uncontrolled pilot in which mothers will receive MB-TXT and fathers will receive a Fathers and Babies (FAB) (*previously referred to as MB DAD*) pilot curriculum developed using existing materials and data collected via qualitative research with HV clients, their partners, and HV staff.

Aim 1. To determine the feasibility and acceptability of conducting the MB-TXT intervention protocol across three HV programs in preparation for a larger fully powered RCT. Using MB text messages already developed by Co-I [name], we will collect data on home visitor adherence to delivering text messages at specified intervals, percentage of clients responding to text messages, and client comprehension of text messages as well as perceptions of text messages' utility.

Aim 2. To calculate a preliminary effect size that could be used, along with other relevant data, to calculate sample size for a future fully powered RCT.

H1. Women receiving MB-TXT will exhibit greater reductions in depressive symptoms, compared to women receiving MB.

H2. Women receiving MB-TXT will experience greater changes in hypothesized intervention mechanisms compared to women receiving MB—specifically, fewer negative cognitions and increased behavioral activation, use of social support networks, and mood regulation.

H3. Women who participate in MB-TXT will report greater completion of personal projects.

Aim 3. To develop and determine the feasibility and acceptability of a) conducting the FAB intervention protocol and b) assessing paternal and dyadic outcomes across two HV

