Focus Groups: There will be six focus groups during the study. Two focus groups with HV supervisors, managers, and home visitors will take place during phase 1 and 2. Four focus groups with clients and their partners will take phase during phase 2. All focus group participants will receive \$30 remuneration in the form of a Northwestern PNC stored-value card (Visa Gift-Card).

Related to Aim 1, MB-TXT feasibility and acceptability data will be collected from clients and home visitors. Similar to previous SMS studies, we will use percentage of text responses as an indicator of "read" messages. We will assess home visitor adherence to the MB-TXT protocol by using archived data from HealthySMS to calculate percentage of texts sent at appropriate intervals, as stated in the MB Instructor Manual. Home visitors will complete a brief web-based REDCap survey after completing each MB session to assess if clients came to the session having completed their personal project. Using a 4-point Likert Scale, home visitors will also ask clients to rate the extent to which each of the 3 intersession texts was a) useful and b) easy to understand; these data will be entered into REDCap. Related to Aim 2, participant outcomes will be collected via survey at baseline and 6 months. Data will be collected and managed using REDCap electronic data capture tools hosted at Northwestern. Participants will receive \$20 remuneration for each assessment. At each assessment, a link to REDCap will be sent to study participants who can complete the assessment on any web platform (smartphone, tablet, and computer). The Project Manager or Research Assistant will complete assessments by phone for participants who prefer not to use REDCap. Depressive symptoms, as measured by the the Beck Depression Inventory-II (BDI)¹⁰⁰ a 21-item self-report measure is our primary outcome. Secondary outcomes, which map onto the hypothesized mechanisms for influence on depressive symptoms are: cognitive structuring (Experiences Questionnaire),⁸⁵ behavioral activation (Behavioral Activation Depression Scale),⁸⁶⁻⁸⁸ social support (MOS Social Support Survey),⁸⁹ and mood regulation (Negative Mood Regulation Scale).^{90,91} We estimate 15% attrition at 6months, resulting in 46 participants per arm; previous MB trials conducted by PI [name] had 12 month attrition rates <10% and we will use similar procedures for minimizing attrition.

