Analysis for Aim 2 is limited to the fact that this is a pilot study. As such, we will compare MB and MB-TXT groups at the individual level (not adjusting for potential clustering effect of either home visitor or HV program). The data will also provide key insights for future studies on how correlated the BDI scores will be over time, as longitudinal data during this postpartum period is not readily available. To address hypothesis 2, the first step in mediation is to determine the mediator's association with the criterion (group), as well as the outcome. The sample provides 80% power to detect effect sizes of 0.59 using two sided Mann Whitney tests at a type I error rate of 5% (for the between group comparison of potential mediators: negative cognitions, behavioral activation, use of support systems, mood regulation), as well as 80% power to detect correlations as small as 0.287 (comparing BDI to

PROTOCOL TITLE: The Mothers and Babies Text Project

the potential mediators). Pilot data will allow us to examine potential ranges of Intraclass Correlation Coefficients (ICC), which we need to account for in a larger RCT. These data will allow us to explore whether randomization should be done at HV program level, or the home visitor level. This sample provides 80% power to detect ICCs of 0.179 (13-14 observations at 10-12 HV programs), or of 0.261 (3 observations in 36 home visitors).

Phase 2 (FAB Development and Pilot)

Study Activities Include:

- Focus Groups with HV Clients (n=16) and their male partners (n=16)
- Development of FAB
- Pilot FAB
- Note: The research team submitted a modification to add/update details about the focus groups for phase 2 of the study. Focus group guide for these groups was submitted a modification for versions 7 of the protocol.
- Note: The research team submitted a modification to add/update details for the FAB intervention pilot in phase 2 of the study including recruitment materials. Modifications are included in version 8 of the protocol.
- FAB Post Intervention Focus Groups and Key Informant Interviews
- Note: The research team will submit a modification to add/update details about the FAB post intervention focus groups and key informant interviews. The modification will include focus and key informant consents, the focus group guide and the key informant interview guide.
-

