6.0 Incomplete Disclosure or Deception: N/A

7.0 Recruitment:

Study Participants: During phase 1, we will recruit 108 study participants from each of the participating HV programs. We will enroll 108 HV clients at 10-12 HV programs, 54 women will receive Mothers and Babies 1-on-1 without text message enhancements and 54 women will receive Mothers and Babies 1-on-1 with text message enhancements. Of the 108 women, 16 will be recruited for focus groups phase 2 of the study.

During phase 2 of the study we will conduct focus groups with the identified 16 women from the 108 group that participated in phase 1 of the study. We will also include their male partners (n=16) in two focus groups of 8 participants. Additionally we will recruit 36 women and their male partners to participate in the FAB Pilot Study.

Home Visitors: We will recruit approximately 36 home visitors from 10-12 participating HV programs throughout the state of Illinois. All HV programs recruit women at high risk for poor pregnancy and/or parenting outcomes via referrals from prenatal care clinics, community outreach, and current program participation. All of the home-visitors who are being recruited through the participating home-visiting sites have been previous trained and are currently implementing Mothers and Babies 1-on-1. Home visitors that have not been trained will receive an in-person training (see training section for more detail). Each home-visitor will identify 1-4 client that will participate in study activities, of these clients 1-2 will receive MB without Text and 1-2 will receive MB with Text. All home-visitors will implement MB without text and MB with text. Programs will initially implement MB 1-on-1 and will recruit MB participants for six months before crossing over to recruit MB-TXT participants for 6 months. To pilot FAB 1-3 home-visitors from each program will identify 1-4 client dyads that will participate in FAB pilot study activities; Home-visitors who will implement FAB will recruit dyads.

We anticipate 16 home-visitors will participate in focus groups during phase 1 and 2 of the study. 10-12 HV programs will be recruited to implement the FAB pilot.

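### The pilot's ICCs are offered as a guide to the next RCT's level of randomization, supported only by power to detect ICCs of 0.179 or 0.261; at this size they cannot reliably separate the two levels and should be reported as estimates with confidence intervals

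*Combined protocol and SAP*

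**What the plan says.** Section 1.0 makes Aim 2 a preparation for a larger trial: the pilot is to yield an effect size that, with other information, will size a fully powered RCT. The Phase 1 analysis text in section 4.0 adds a second product. It expects the data to show a plausible span of ICCs, says a larger RCT must allow for them, and continues: "These data will allow us to explore whether randomization should be done at HV program level, or the home visitor level".

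The next sentence is the only statement of how well the pilot can do this: "This sample provides 80% power to detect ICCs of 0.179 (13-14 observations at 10-12 HV programs"), "or of 0.261 (3 observations in 36 home visitors"). No alpha is given for the ICC test; the nearest stated level is for the mediator comparisons, "two sided Mann Whitney tests at a type I error rate of 5"%. The text names no outcome or visit for the ICC, no expected value, no confidence interval, and no rule linking an ICC to a level of randomization.

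On sample size, section 1.0 states "In Phase 1, we will recruit 108 pregnant women for a RCT" and section 4.0 states "We estimate 15% attrition at 6months, resulting in 46 participants per arm". On delivery, section 7.0 states "All home-visitors will implement MB without text and MB with text". Earlier in section 4.0, limiting contamination is the reason given for allocating this trial by program.

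**The concern.** Power to reject a zero ICC answers a question that the next trial does not ask. Its designers will need to know how large the program and home-visitor ICCs could plausibly be, and how well that is known. A detection statement gives neither, and it leaves unsaid how a small or non-significant estimate should be read. Failing to detect an ICC is not evidence that clustering can be ignored.

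The stated thresholds, 0.179 and 0.261, are large. If the true ICCs are much smaller, the estimates will scatter around zero, and which of the two comes out larger will be largely chance. An ICC also does not measure contamination, and contamination bears directly on whether one home visitor can safely deliver both conditions. What is at stake is the quality of a stated deliverable of Aim 2. No Phase 1 comparison or participant is affected.

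**Working it through.** **Inputs.** 108 women enrolled (section 1.0). 15% attrition: 54 × 0.85 = 45.9, so 46 per arm and 92 in all (section 4.0). 10-12 programs and about 36 home visitors (section 7.0). Assumptions: an upper-tailed 5% test, equal cluster sizes, and true ICCs of 0.02 to 0.10, since the documents give none.

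**Formulas.** One-way random-effects ANOVA with k clusters of n women and ICC ρ. Let λ = 1 + nρ/(1 − ρ). Then F/λ follows F(k − 1, k(n − 1)).
- Power = P(F(k − 1, k(n − 1)) > F₀.₉₅/λ).
- The ICC estimate is (F − 1)/(F + n − 1), so it is zero or below when F ≤ 1. That has probability P(F(k − 1, k(n − 1)) ≤ 1/λ).

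**1. Reproducing the plan's figures (108 women).**
- 36 visitors × 3: λ at 0.261 is 1 + 3 × 0.261/0.739 = 2.06. With F₀.₉₅(35, 72) = 1.586, power is 80.1%. The detectable ICC is 0.261, an exact match.
- Programs: 108 women over 10-12 programs give 0.178-0.182, which matches 0.179. The printed layout of 13-14 women at each of 10-12 programs would mean 130-168 women and a threshold of 0.121-0.150. The figure therefore fits 108 women but not the printed layout, and the two should be reconciled.

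**2. The same test with 92 women.**

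| Level | 80%-power ICC | Power at the stated ICC |
|---|---|---|
| 10-12 programs | 0.205-0.210 | 72-74% at 0.179 |
| 36 home visitors | 0.307 | 68% at 0.261 |

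**3. Behaviour of the estimate with 92 women.** Worked example at ρ = 0.05:
- 11 programs, n = 92/11 = 8.36: λ = 1 + 8.36 × 0.05/0.95 = 1.44, 1/λ = 0.694, and P(F(10, 81) ≤ 0.694) = 27%.
- 36 visitors, n = 92/36 = 2.56: λ = 1.135, 1/λ = 0.881, and P(F(35, 56) ≤ 0.881) = 35%.

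| Assumed true ICC | Programs: estimate ≤ 0 | Programs: power | Visitors: estimate ≤ 0 | Visitors: power |
|---|---|---|---|---|
| 0.02 | 42% | 10-11% | 44% | 7% |
| 0.05 | 27% | 21-23% | 35% | 11% |
| 0.10 | 13% | 43-46% | 22% | 21% |

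At 0.05 the central 95% of estimates runs from about −0.07 to 0.21 (programs) and −0.18 to 0.29 (visitors).

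**4. A result that assumes no true ICC.** If the pilot's estimate were exactly zero, then F = 1. The upper limit of the two-sided 95% interval is (F_U − 1)/(F_U + n − 1), with F_U = 1/F₀.₀₂₅(k − 1, k(n − 1)). For 11 programs F_U is about 3.17, so the limit is 2.17/(3.17 + 7.36) = 0.21. For 36 visitors F_U is about 1.87, so the limit is 0.87/(1.87 + 1.56) = 0.25.

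**5. Ranking the two levels.** A nested simulation used 12 programs × 3 visitors × 3 women, which is all 108. With true variance components of 0.05 at one level and 0.01-0.02 at the other (assumed), the larger component came out larger in only about 56-62% of runs.

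Unequal caseloads (section 7.0 allows 1-4 clients per visitor) would widen these ranges further.

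**The case against.** The strongest reply is that the plan claims little. A reader might infer that it commits to choosing the level from the ICC. It does not: the verb is explore, there is no decision rule, and the Aim 2 text opens by calling itself limited because this is a pilot. That reply stands.

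Other stronger readings also fail.
- **That nothing below 0.179 or 0.261 can be detected.** These are 80%-power points, not limits. At a true ICC of 0.10, program-level power is 50-53% with 108 women and 43-46% with 92.
- **That a zero ICC would be taken into the next trial as no inflation.** Nothing says so. Section 4.0 says ICCs must be allowed for, and section 1.0 says other data will also inform the sample size.
- **That contamination has been overlooked.** Section 4.0 gives it as the ground for allocating this trial by program. Visitors delivering both conditions is a feature of this pilot's sequential crossover, not a plan for the next RCT.
- **That the next trial's size would be badly wrong.** The documents give no future cluster size. With ICC 0.05, an assumed program cluster of 20 has design effect 1 + 19 × 0.05 = 1.95, but 3 women per visitor gives only 1 + 2 × 0.05 = 1.10.

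It is also fair that a pilot protocol need not fix the design of a later trial, that the ICC is a legitimate input on efficiency, and that a two-level model on the same women will be just as imprecise. The last point supports reporting the interval, because the interval is what shows the imprecision.

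**Conclusion.** The concern holds in a limited form. The plan proposes to explore the level of randomization with these ICCs and supports that only with a detection claim. The claim is correct for 108 women but optimistic for a 6-month outcome, where 92 are expected: about 0.205-0.210 rather than 0.179, and 0.307 rather than 0.261. If the ICC is meant for a baseline measure, the 108-woman figures stand; the text does not say which is meant.

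The frequency of zero or negative estimates depends on the assumed ICC: 13-42% for programs and 22-44% for visitors over 0.02-0.10. The upper limit of about 0.21 to 0.25 after a zero estimate needs no such assumption. Together with a ranking that is right little more often than a coin toss under the assumed components, it shows that the pilot cannot reliably separate the two levels. All of this rests on equal clusters, a one-way ANOVA and a one-sided 5% test that the plan does not itself state. It is a worthwhile improvement to how Aim 2 is reported, not a defect in the Phase 1 comparison.

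**What to change.** In the Aim 2 analysis text of section 4.0:

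1. Replace the power-to-detect sentence with an estimation plan that names the outcome and visit. Fit one model with random effects for program and for home visitor within program and a fixed term for arm, and report both ICCs with 95% confidence intervals.
2. Estimate the same ICCs on baseline BDI, which uses all 108 women and has no arm effect. Treat this as a supplement, because it cannot show clustering that arises from delivery.
3. State that a non-significant ICC will not be read as zero.
4. State that the ICCs are too imprecise to settle the level of randomization alone, and will be weighed with contamination, delivery data and ICC values from outside the pilot.
5. Reconcile the printed 13-14 observations per program with 108 women over 10-12 programs.

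The cost is wording plus one model, fitted at baseline and at 6 months to data already being collected. The pilot's claim about ICCs becomes more modest.

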FAB. The male study participants (n=36) will receive FAB a text based intervention/curriculum. PI [name], Co-Investigator [name], and the Research Project Manager have developed a curriculum that aligns and is complimentary to MB 1-on-1 plus MB-TXT. The first FAB session can be delivered in person with the dyad (female and male client) during a home visit, or separately. If the male client cannot be present for the first session, the Home Visitor or Project Manager will deliver the session over the phone. After the first session is initiated with the dyad, the female client will receive MB 1-on-1 and MB-TXT and the male client will receive FAB texts (9-15 per module). The HV will have flexibility to deliver additional sessions in to the male client but is not required. Text messages to complement MB content (English Only). These texts focus on: a) skill reinforcement b) practice reminders (c) self-monitoring. These texts will be linked with the 12 MB sessions that the female client is receiving but the male partner will receive additional texts to deliver the content in a text-based sessions. He will receive 3-6 text messages per session while his partner will receive 3 messages after each session. Specifically, after completing each in-person session, texts will be sent by a home visitor to both her female client (Total # of Txts = 36) and her partner (Total # of Txts = 51).

We anticipate that texts will be sent within one week of the completion of a session to ensure standardization and minimize the likelihood that home visitors will forget to send messages. All texts will be sent through the HealthySMS platform used in Co-I [name]'s pilot study. To increase participant engagement (i.e., reading texts), messages will be sent at different times of the day, per the study participant's preference.⁶⁴ Each text and related response are linked and stored in HealthySMS for immediate access and review or future download and analysis.

We have budgeted for each dyad to receive a monthly stipend to cover the costs of text messaging until the 12 MB sessions are completed or up to six months post baseline. In phase 1 (MB-TEXT) this is available to only participants receiving texts. If participants do not cell phones with unlimited texting to ensure access to necessary technology.

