Training and Supervision of HV programs. All the participating HV programs have been trained on MB 1-on-1 and are currently implementing the curriculum. All programs will receive a two-hour training on implementing FAB and MB-TXT conducted by the Research Project Manager. All programs will receive supervision after the first implementation of the intervention begins at the HV programs.

Participant Screening: Participants will initially be screened for eligibility criteria by their home visiting program sites. Upon permission from the potential study participant, program sites will fill out a referral form, which will include the potential study participants name and contact information, and send it to the research team (e-mail or fax). The HV will explain the study and provide brochures for both the female client and male partner with study details during the referral process. Once the program sites refer potential study participants, a member of the study team will call the participants using the "Phone Script for Referrals" to screen the potential study participants for eligibility criteria and move forward with the consent process either via telephone or a REDCap survey link. The female client and male partner will be contacted and consented separately. The female and male client will both have to agree to participate in the study to be eligible to participate. If there is discordance, (female client or male partner does not agree) to participate the dyad will be ineligible. Our informed consent from includes an option to be contacted for future research studies, we will only contact participants who indicate "yes" to this option for qualitative data collection activities (focus groups and key informant Interviews) after completing FAB.

Participant Outcomes Surveys:

Clients FAB: Participant outcomes will be collected at three time points—baseline and 3 and 6 months post- intervention. Participants will receive \$20 remuneration and will be in the form of a Northwestern PNC stored-value card (Visa Gift-Card).

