We will measure male clients’ perceived utility and comprehension of text messages by asking clients to rate the extent to which the text messages were a) useful, b) enjoyable, and c) easy to understand. Questions will be on a 4-point Likert Scale and will be asked of clients at the end of each MB module (Introduction, Pleasant Activities, Thoughts, Contact with Others and Review/Conclusion). We will measure male and female clients’ perceived feasibility and acceptability post intervention. These data will be collected via REDCap.

Home Visitors: Home visitors will be asked to respond to a REDCap survey items after completing each MB session to assess if female clients came to the session having completed their personal project, implemented session, and next scheduled session date. Home visitors will measure female clients’ perceived utility and comprehension of text messages by asking clients to rate the extent to which each of the 3 text messages received between sessions was a) useful and b) easy to understand. Questions will be on a 4-point Likert Scale and will be asked of clients at the end of each MB session. These data will be inputted into the HealthySMS system. We will assess home visitors’ perceived feasibility and acceptability post intervention after all 12 session of MB-TXT and FAB are completed.. These data will be collected via REDCap.

Focus Groups: There will be three focus groups and 4 key informant interviews during the study and will take place during phase 2 after participants have completed FAB. All focus group and key informant participants will receive \$35 remuneration in the form of a Northwestern PNC stored-value card (Visa Gift-Card).

Table 1: Detailed Description of Study Measures for Phase1

Text messages read by HV clients will be measured by calculating the percentage of text messages responded to by clients.
Home Visitor Adherence to MB-TXT protocol will be measured by using the archived data from HealthySMS to calculate the percentage of texts sent at the appropriate intervals, as stated in the MB Instructor Manual
Client completion of personal projects will be measured by asking home visitors to respond to a REDCap survey item after completing each MB session to assess if clients came to the session having completed their personal project.

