
Mood regulation will be measured using the Negative Mood Regulation Scale (NMRS).⁹⁰ The NMRS assesses an individual’s expectancy that some behavior or cognition will alleviate a negative mood state. For each question, respondents use a five-point scale from “very much disagree” to “very much agree” to indicate what they believe they can do when they are disappointed or experiencing a negative mood. The scale has demonstrated excellent internal consistency, good test-retest reliability, and correlational evidence of both convergent and discriminant validity with constructs such as depressive symptoms and locus of control, respectively.⁹¹

Mothers and Babies Skill Utilization will be assessed using items developed the study investigators.

Client demographics will be assessed using items developed by the study investigators. Baseline Demographics –17 items 3 & 6 month Follow-up Demographics – 8 items

Prenatal Behavior and Service Utilization. - will be assessed using items developed by the study investigators.

Table 2: Detailed Description of Study Measures for Phase 2

Text messages read by HV clients will be measured by calculating the percentage of text messages responded to by female and male study participants.

Home Visitor Adherence to MB-TXT protocol will be measured by using the archived data from HealthySMS to calculate the percentage of texts sent at the appropriate intervals, as stated in the MB Instructor Manual.

HV Post Intervention Survey will be assessed using questions developed by the study investigators. Questions will be on a 4-point Likert Scale and will be asked of home visitors at the end of the 12 MB sessions.

Female Client perceived utility and comprehension of text messages will be measured by asking home visitors to rate the extent to which each of the 3 text messages received between sessions was a) useful and b) easy to understand. Questions will be on a 4-point Likert Scale and will be asked of clients at the end of each MB session. These data will be inputted into HealthySMS.

Female Client Post Intervention Survey will be assessed using questions developed by the study investigators. Questions will be on a 4-point Likert Scale and will be asked of the female clients at the end of the 12 MB sessions.

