
Male Partner perceived utility and comprehension of text messages will be measured by a survey to rate the extent to which the text messages received were a) useful and b) easy to understand. Questions will be on a 4-point Likert Scale and will be asked of clients at the end of each MB module.

Male Partner Post Intervention Survey will be assessed using questions developed by the study investigators. Questions will be on a 4-point Likert Scale and will be asked of male partners at the end of the 12 MB sessions.

Depressive Symptoms will be assessed using the Beck Depression Inventory-II (BDI),¹⁰⁰ a 21-item self-report measure of depressive symptoms to assess severity of depressive symptoms consistent with DSM-IV symptom criteria. The BDI has excellent internal reliability for outpatient samples and its construct validity has been established.

Anxiety symptoms will be assessed using the GAD-7- To assess anxiety, we will administer the Generalized Anxiety Disorder 7-item scale (GAD-7; Spitzer et al., 2006), which is a widely used self-report measure of anxiety symptoms.

Perceived stress will be assessed using the Perceived Stress Scale 10-item version. We will use the 10-item Perceived Stress Scale (PSS-10; Cohen & Williamson, 1988; Remor et al., 2006) to assess the level to which an individual considers their life stressful and how controllable a

person appraises her life.

Social Support will be assessed using the NIH Toolbox Instrumental Support and Emotional Support measures. Each measure asks 8 questions and asks respondents to indicate the extent to which they have received support for each area in the last month.

Mothers and Babies Skill Utilization will be assessed using items developed the study investigators.

Client demographics will be assessed using items developed by the study investigators. Female Client Baseline Demographics- 18 items Female Client 3 & 6 Follow-Up Demographics- 10 items Male Partner Baseline Demographics – 14 items Male Partner 3 & 6 Follow-Up Demographics- 8 items

Prenatal Behavior and Service Utilization. - will be assessed using items developed by the study investigators.

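### Phase 2 end-of-programme surveys and post-FAB father interviews are tied to completion, so overall feasibility and acceptability views come from completers only

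*Combined protocol and SAP*

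**What the plan says.** Aim 3 (Section 1.0) and the overview of Phase 2 (Section 4.0) make the feasibility and acceptability of FAB a purpose of the 36-dyad uncontrolled pilot.

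Table 2 in Section 4.0 lists three post-intervention surveys with one common trigger:

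- Male partner: the questions "will be asked of male partners at the end of the 12 MB sessions".
- Female client: the questions "will be asked of the female clients at the end of the 12 MB sessions".
- Home visitor: the questions "will be asked of home visitors at the end of the 12 MB sessions". The Home Visitors paragraph under the Phase 2 Participant Outcomes Surveys puts this assessment "post intervention after all 12 session of MB-TXT and FAB are completed".

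For clients, the same part of Section 4.0 is looser. It plans to measure "perceived feasibility and acceptability post intervention" and gives no rule for a dyad that stops.

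The post-FAB focus groups and key informant interviews "will take place during phase 2 after participants have completed FAB". The Phase 2 Participant Screening paragraph likewise limits contact to people who agreed to it, "for qualitative data collection activities (focus groups and key informant Interviews) after completing FAB". Section 12.0 divides the 22 fathers into 18 focus group participants and 4 key informants.

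Other Phase 2 measures run during the intervention: women's ratings of the texts at each session, men's ratings at each module, the percentage of texts answered by both, and home visitor adherence from the HealthySMS archive.

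**The concern.** In a feasibility pilot, the participants who disengage are among the most informative. If the only overall judgements come from dyads who reached session 12, those who found the programme least workable are missing by rule and not by chance. The resulting acceptability figure probably looks better than it would for everyone enrolled.

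The father interviews have the same gap. Section 4.0 wants them to show which parts of FAB need changing and how to engage fathers better. Fathers whom FAB did not hold are well placed to answer that, and the completion rule leaves them out.

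The father's position is also dependent on his partner's. His texts are linked to her sessions and his ratings to the ends of her MB modules. If she stops, his later ratings and his final survey lose their trigger, even if he would have carried on.

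**Working it through.** The plan states no figure that can be reproduced here; the point concerns when measures are taken. The first step is to set the Phase 2 feasibility and acceptability measures side by side.

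| Measure (Section 4.0) | When taken | Available from a dyad that stops early? | Overall judgement or reason for stopping? |
|---|---|---|---|
| Three post-intervention surveys | End of 12 sessions | No trigger stated | Overall judgement intended |
| Father focus groups and interviews | After completing FAB | No trigger stated | Overall judgement and suggested changes |
| Women's text ratings | Each session | Yes, up to stopping | No: useful, easy to understand |
| Men's text ratings | Each module | Yes, for modules finished | No: useful, enjoyable, easy to understand |
| Percentage of texts answered | Continuous | Yes, up to stopping | No |
| Home visitor adherence | From archive | Yes, up to stopping | No: describes sending |

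The 3- and 6-month assessments collect outcomes; Table 2 does not schedule the acceptability surveys at them. No section gives a date-based trigger, an exit survey or an exit interview.

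**What an early stopper contributes.** Section 4.0 (Study Conditions, MB 1-on-1) gives modules of 2, 3, 3, 3 and 1 sessions: 2 + 3 + 3 + 3 + 1 = 12. A dyad that stops after session 5 has finished 2 + 3 = 5 sessions, which is two modules. The father has reached two of five rating points, and the woman has had several session ratings. A man whose partner stops before the end of the first module gives no rating, and texts sent after a woman's last attended session go unrated.

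**Interview places.** 18 + 4 = 22, which agrees with the stated total. 22/36 = 61%. Under a completers-only rule, fewer than 22 completing fathers would put the target out of reach, before allowing for those who declined further contact.

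**How much completers alone can leave open.** Phase 2 completion is not given, so it is assumed. Let *n* of 36 dyads complete, all of them respond, and *k* be favourable. The observed proportion is *k*/*n*. Over all 36, the lower bound is *k*/36 (no stopper favourable) and the upper bound is (*k* + 36 − *n*)/36 (every stopper favourable). Taking about 90% of completers as favourable:

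| *n* complete | Observed | Lower bound | Upper bound |
|---|---|---|---|
| 31 (about 85%) | 28/31 = 90% | 28/36 = 78% | (28 + 5)/36 = 92% |
| 27 (75%) | 24/27 = 89% | 24/36 = 67% | (24 + 9)/36 = 92% |
| 18 (50%) | 16/18 = 89% | 16/36 = 44% | (16 + 18)/36 = 94% |

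The room for error is lopsided. With 27 completers, the all-dyad figure can lie 88.9 − 66.7 = 22.2 points below the observed value but only 91.7 − 88.9 = 2.8 points above it. These bounds assume nothing about stoppers' views. They apply to the end-of-programme surveys and not to the interim ratings.

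**The case against.** The best reply is that early stoppers are not silent. A reader might infer from Table 2 that they are never asked anything and that all Aim 3 acceptability data come from completers. The documents do not support that. Women rate texts session by session, men rate them module by module, and usage and adherence are recorded throughout. For Phase 1, Section 4.0 introduces measures of the same kind as feasibility and acceptability data. FAB is itself delivered mainly by text, so a man's rating of a module's texts says a good deal about that part of the programme, and one of his items is enjoyment. This stands, and it confines the point to overall judgements, reasons for stopping and the father interviews.

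A second reply is that the trigger is less absolute than Table 2 suggests. The client wording elsewhere in Section 4.0 and the Participant Outreach and Contact list name a post-intervention point without defining it by session 12. Some passages describe the 22 men as having received FAB. A home visitor with several dyads may still be surveyed because another dyad finishes. This stands in part: the plan states no deliberate exclusion. But the only explicit definitions point to completion, and nothing extends them to non-completers.

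A reader might also take the stipend wording, "until the 12 MB sessions are completed or up to six months post baseline", as showing that the protocol expects dyads to drop out. It is a limit on payment, and a dyad still in progress at six months has not stopped.

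Finally, no acceptability threshold or progression rule is stated for Phase 2, so no planned decision is shown to be wrong. That limits the weight of the point but does not answer it.

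**Conclusion.** The point holds in this form: as written, the three end-of-programme surveys and the 22 father places draw on completers only, and early stoppers are represented only by interim ratings and usage data. Upward bias in end-of-programme acceptability is probable, on the assumption that those who stop tend to be less favourable than those who finish.

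Its size cannot be established. The documents give neither a Phase 2 completion rate nor any acceptability rate, so a specific number of points of bias is not supported. The case of 27 completers (89% observed, 67% to 92% possible) is an illustration that also assumes every completer responds. If nearly all 36 dyads finish, the problem largely disappears. This is a cheap improvement to the pilot and not a defect that invalidates it.

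**What to change.** 1. Send all three surveys for every enrolled dyad at the earliest of session 12, the date sessions stop, or a fixed date such as six months post baseline, a cut-off the protocol already uses for the stipend. Send the father's link even if his partner has stopped.
2. Add one item on the reason for stopping. Sessions received need no new item, since home visitors already log them after each session.
3. Report response counts out of all 36 dyads, split results by completers and early stoppers, and give best- and worst-case bounds for non-respondents as above.
4. Open some of the existing 22 father places to men who stopped early and agreed to future contact.
5. Use one definition of the post-intervention point in Table 2, the survey paragraphs and the contact list.

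The cost is a changed REDCap trigger, one survey item and edits to the text, with no additional participants. Response among early stoppers will be lower and the acceptability figure probably less favourable, but both will then be visible.
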